### 17.7. Instructions Related to Severe Acute Respiratory Syndrome Coronavirus 2 (SARS-CoV-2)

Due to the potential impact of SARS-CoV-2, ie COVID-19, on subject safety, the Sponsor recommends the following dose modification and management plan for subjects with confirmed or suspected SARS-CoV-2 while being treated with DS-8201a. Dose modifications will be based on the worst CTCAE grade. Use CTCAE version 5.0 general grading criteria to evaluate SARS-CoV-2. All dose modifications (discontinuation, interruptions or reductions) must be recorded on the AE and drug administration eCRFs.

#### Dose Modification Criteria for Suspected or Confirmed SARS-CoV-2

If SARS-CoV-2 infection is suspected, interrupt DS-8201a and rule out SARS-CoV-2 per local guidance.

- If SARS-CoV-2 is ruled out, follow dose modification and management guidance as outlined in [Table 17.4](#).
- If SARS-CoV-2 is confirmed or is still suspected after evaluation follow dose modification as outlined in [Table 17.4](#) below and manage SARS-CoV-2 per local guidance until recovery of SARS-CoV-2. SARS-CoV-2 recovery is defined as no signs/symptoms of SARS-CoV-2, at least 1 negative real-time reverse transcription polymerase chain reaction (RT-PCR) test result, and nearly or completely resolved chest CT findings.

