**Table 3.2: Actions Taken for Pulmonary Toxicity**

Worst toxicity NCI-CTCAE version 4.03 Grade (unless otherwise specified)	Management Guidelines for DS-8201a
Pulmonary Toxicity	
	
If a subject develops radiographic changes potentially consistent with ILD or develops an acute onset of new or worsening pulmonary or other related signs/symptoms such as dyspnea, cough or fever, rule out ILD/pneumonitis. If the AE is confirmed to have an etiology other than ILD/pneumonitis, follow the management guidance outlined in the “Other Non-Laboratory Adverse Events” dose modification section below.
 
If the AE is suspected to be ILD/pneumonitis, treatment with study drug should be interrupted pending further evaluations. Evaluations should include:
 
 
• High resolution CT
 
• Pulmonologist consultation (infectious disease consultation as clinically indicated)
 
• blood culture and CBC (other blood tests could be considered as needed)
 
• bronchoscopy and bronchoalveolar lavage if clinically indicated and feasible should be considered
 
• Pulmonary function tests and pulse oximetry (SpO2).
 
• Arterial blood gases if clinically indicated
 
• One blood sample collection for PK analysis as soon as ILD/pneumonitis is suspected, if feasible.
 
 
Other tests could be considered, as needed.
 
If the AE is confirmed to be ILD/pneumonitis, follow the ILD management guidance as outlined below. All events of ILD regardless of severity or seriousness will be followed until resolution including after drug discontinuation.

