Grade 1	
The administration of trastuzumab deruxtecan must be interrupted for any ILD events regardless of grade.
 
 
• Monitor and closely follow-up in 2 to 7 days for onset of clinical symptoms and pulse oximetry
 
• Consider follow-up imaging in 1-2 weeks (or as clinically indicated).
 
• Consider starting systemic steroids (e.g. at least 0.5 mg/kg/day prednisone or equivalent) until improvement, followed by gradual taper over at least 4 weeks.
 
• If worsening of diagnostic observations despite initiation of corticosteroids, then follow Grade 2 guidelines.*
 
 
For Grade 1 events, trastuzumab deruxtecan can be restarted only if the event is fully resolved to Grade 0:          If resolved in ≤ 28 days from day of onset, maintain dose          If resolved in > 28 days from day of onset, reduce dose 1 level          However, if the event grade 1 ILD occurs beyond cycle day 22 and has not resolved within 49 days from the last infusion, the drug should be discontinued.          * If patient is asymptomatic, then patient should still be considered as Grade 1 even if steroid treatment is given

Grade 2	
Permanently discontinue subject from study treatment
 
 
• Promptly start and treat with systemic steroids (e.g., at least 1mg/kg/day prednisone or equivalent) for at least 14 days or until complete resolution of clinical and chest CT findings, then followed by a gradual taper over at least 4 weeks.
 
• Monitor symptoms closely.
 
• Re-image as clinically indicated.
 
• If worsening or no improvement in clinical or diagnostic observations in 5 days,             
 
• Consider increasing dose of steroids (e.g., 2 mg/kg/day prednisone or equivalent) and administration may be switched to intravenous (e.g. methylprednisolone).
 
• Re-consider additional work-up for alternative etiologies as described above.
 
• Escalate care as clinically indicated.
 
 
 

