**Table 17.4: SARS-CoV-2 Dose Modification Criteria**

SARS-CoV-2 Worst Toxicity NCI-CTCAE Version 5.0 Grade (unless otherwise specified)	Schedule Modification for DS-8201a
Grade 1	Resume study drug at the same dose a
Grade 2	Resume study drug at the same dose if chest CT findings are completely resolved a Reduce by 1 dose level if chest CT findings are nearly resolved
Grade 3	Reduce by 1 dose level if chest CT findings are completely resolved Discontinue study drug if chest CT findings are not completely resolved

SARS-CoV-2 = severe acute respiratory syndrome coronavirus 2 (SARS-CoV-2); CT = computed tomography

a Closely monitor signs/symptoms after resuming DS-8201a, initially with a phone call every 3 days for the first week, and then with a weekly phone call thereafter, for a total of 6 weeks.

In addition to the recommendations outlined in [Table 17.4](#), Investigators may consider dose modifications of the study drug according to the subject's condition and after discussion with the study Medical Monitor or designee.

If an event is suspected to be drug-related ILD, manage per protocol ILD management guideline (Table 3.2).

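### Section 17.7 and Table 3.2 do not assign a lung event with possible SARS-CoV-2 to one set of dose rules

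*Combined protocol and SAP*

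**What the plan says.** **Section 17.7 (SARS-CoV-2).** The opening step is: "If SARS-CoV-2 infection is suspected, interrupt DS-8201a and rule out SARS-CoV-2 per local guidance". After evaluation: "If SARS-CoV-2 is confirmed or is still suspected after evaluation follow dose modification as outlined in" Table 17.4, with management continuing until recovery. "SARS-CoV-2 recovery is defined as no signs/symptoms of SARS-CoV-2, at least 1 negative real-time reverse transcription polymerase chain reaction (RT-PCR) test result", together with chest CT findings that have nearly or completely resolved. The bullet before it sends subjects in whom infection has been ruled out to Table 17.4 too.

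Table 17.4 works by CTCAE version 5.0 grade:
- Grade 1 resumes at the same dose.
- Grade 2: "Resume study drug at the same dose if chest CT findings are completely resolved"; if CT is only nearly resolved, the dose drops one level.
- Grade 3 drops one level if CT is completely resolved, and otherwise stops.

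Below the table: "If an event is suspected to be drug-related ILD, manage per protocol ILD management guideline (Table 3.2").

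**Section 3.2.5.2, Table 3.2 (pulmonary toxicity).** Radiographic changes potentially consistent with ILD, or acute new or worse pulmonary or related symptoms, start a work-up to rule out ILD/pneumonitis. Drug is interrupted while ILD/pneumonitis is suspected. "If the AE is confirmed to have an etiology other than ILD/pneumonitis, follow the management guidance outlined in" the section for other non-laboratory adverse events. The graded ILD actions apply once ILD/pneumonitis is confirmed. At Grade 1, "trastuzumab deruxtecan can be restarted only if the event is fully resolved to Grade 0"; from Grade 2, "Permanently discontinue subject from study treatment". Grading is by CTCAE version 4.03.

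**Section 5.4.2, Table 5.2, other non-laboratory adverse events.** At Grade 3, dosing waits for resolution to Grade 1 or lower, or to baseline. The dose is then kept if resolution took 7 days or less, and reduced one level if it took longer.

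**The concern.** Both sets of rules can apply to the same subject. Table 3.2 is triggered by chest imaging changes and respiratory symptoms. Section 17.7 does not list its symptoms, but it uses chest CT to define recovery and to set the dose action. A subject with new lung findings and possible infection therefore falls under both.

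The thresholds differ. A suspicion of infection that survives evaluation is enough to enter Table 17.4; leaving the ILD work-up takes a confirmed alternative. The hand-over back to Table 3.2 depends on the investigator suspecting that ILD is drug-related, whereas Table 3.2 speaks of ILD/pneumonitis without that condition.

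What is at stake is consistent re-treatment after a lung event. ILD/pneumonitis is described as an important identified risk (Section 3.2.5.2) and is one of the two AESI categories (Section 8.3). AEs and AESIs leading to discontinuation are among the primary safety endpoints (Section 2.3.1). If two sites can follow the protocol faithfully and manage the same event differently, part of that count reflects which section was opened.

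**Working it through.** There is no planned figure to reproduce and no formula for the conflict itself. The check takes each diagnostic state in turn and reads off what each section directs.

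| State of the event | Table 3.2 | Section 17.7 / Table 17.4 | Consistent? |
|---|---|---|---|
| 1. ILD confirmed | Graded ILD actions | Hands over to Table 3.2 if suspected drug-related | Yes, if regarded as drug-related |
| 2. SARS-CoV-2 and drug-related ILD both suspected | Interrupted pending evaluation | Hands over to Table 3.2 | Yes |
| 3. SARS-CoV-2 still suspected, no cause confirmed, drug-related ILD not specifically suspected | Interrupted while ILD/pneumonitis is suspected; only written release is a confirmed other etiology | Table 17.4: resume, reduce or stop after recovery | No |
| 4. SARS-CoV-2 confirmed as the cause | Other non-laboratory adverse events (Table 5.2) | Table 17.4 | No |
| 5. SARS-CoV-2 ruled out, cause open | ILD work-up continues | Table 17.4 | No |

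**State 3.** Table 3.2 supplies no exit and no graded action. Table 17.4 supplies a dose rule. At Grade 1 it attaches no CT condition of its own, so recovery with nearly resolved CT is enough to resume at the same dose. At Grade 2, nearly resolved CT allows resumption one level lower. The divergence is between staying interrupted and being able to resume.

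**State 4.** Take a Grade 3 event that resolves to Grade 1 or lower within 7 days. The route through Table 3.2 to Table 5.2 keeps the dose. Table 17.4 reduces it one level if CT is completely resolved and stops treatment if not. No branch of Table 17.4 keeps the dose at Grade 3, so the two routes cannot agree for this event. The versions also differ (5.0 general criteria for SARS-CoV-2, 4.03 for Tables 3.2 and 5.2), so even the grade may not carry across.

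**State 5.** Ruled out, confirmed and still suspected all lead to Table 17.4. The sentence on suspected drug-related ILD is the only way out of it. A table of SARS-CoV-2 grades has no evident meaning for a subject shown not to have the infection, so this looks like a wrong cross-reference.

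**Scale of one event.** Section 11.8 plans about 12 subjects and Section 4.3 allows no replacement. With 12 treated, one subject is 1/12 = 8.3 percentage points of any safety-set proportion. The number of events likely to fall in states 3 to 5 is not given and cannot be derived.

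**The case against.** The strongest reply has four parts.

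*Precedence is largely stated.* Suspicion of drug-related ILD is enough to send an event to Table 3.2, and both sections interrupt drug at the outset. This stands for state 2. It does not reach state 3, where the investigator favours infection and so never triggers the hand-over, yet has not met Table 3.2's condition for release.

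*Table 17.4 is not a licence to resume.* It follows a recovery that requires no signs or symptoms and a negative RT-PCR as well as the CT criterion, and Grade 3 can end in discontinuation. This also stands, and it limits the concern. It does not settle which table applies.

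*Section 17.7 is the specific rule.* Sections 5.4 and 5.4.2 point to it for SARS-CoV-2, so a reader may treat it as overriding the general row in Table 5.2. That is a reasonable reading of state 4, but no sentence says so, and Table 3.2 names a different destination.

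*The analysis is descriptive.* No test or decision rule turns on one case (Section 11.4.3). That is correct; the consequence lies in treatment consistency and in the reading of small counts.

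A reader might go further and infer that one unresolved event is permanently stopped under Table 3.2 and re-treated under Table 17.4. The documents do not support that. Permanent discontinuation under Table 3.2 requires confirmed ILD, and a grade-for-grade comparison of the two tables sets confirmed ILD against a SARS-CoV-2 event on a different grading version.

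A reader might also infer that events coded as SARS-CoV-2 escape ILD adjudication. The preferred-term list that triggers data collection is not in the documents, and Section 8.3.1 gives the committee all potential ILD/pneumonitis cases, so this cannot be shown.

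**Conclusion.** The routing is ambiguous in three places: an event with neither cause confirmed and drug-related ILD not specifically suspected; a confirmed SARS-CoV-2 lung event; and a subject in whom SARS-CoV-2 has been ruled out. In the first, the same event is held under one rule and may resume under the other. In the second, a Grade 3 event resolving within 7 days necessarily receives different dose actions. The third appears to be a cross-reference error.

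The size is not estimable. It is tempting to take the 5 of 148 subjects with pneumonitis or ILD in Section 1.2.3 (3 + 2, or 3.4%) and compute 1 − (143/148)^12 = 34%. That is the chance of at least one ILD or pneumonitis case among 12 subjects. It assumes a rate pooled over doses from 0.8 to 8.0 mg/kg applies here, and it says nothing about how often an event would fall between the two tables. It should not be used to size this point.

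The conclusion rests on the text alone and assumes no other study document sets the order of precedence. The separate manuals and monitoring plan are not available here.

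**What to change.** The sponsor must reconcile Table 3.2, the other non-laboratory rows of Table 5.2, the Section 17.7 bullets, and the closing sentence under Table 17.4. The reconciled text should:

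1. use the same condition for leaving the ILD pathway in both sections (confirmed or suspected other cause);
2. use the same hand-over trigger in both (ILD/pneumonitis, or drug-related ILD);
3. state which table governs while both diagnoses are open, and which governs confirmed SARS-CoV-2;
4. say which CTCAE version grades a lung event that moves between the tables;
5. correct the cross-reference for subjects in whom SARS-CoV-2 is ruled out.

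Which clinical rule should prevail is for the sponsor and its clinical advisers; no view is given here.

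The cost is wording in a protocol amendment, with the approvals that Section 15.7 requires. It needs no new assessment, data item, committee or change in sample size.

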**Table 17.4: SARS-CoV-2 Dose Modification Criteria**

SARS-CoV-2 Worst Toxicity NCI-CTCAE Version 5.0 Grade (unless otherwise specified)	Schedule Modification for DS-8201a
Grade 1	Resume study drug at the same dose a
Grade 2	Resume study drug at the same dose if chest CT findings are completely resolved a Reduce by 1 dose level if chest CT findings are nearly resolved
Grade 3	Reduce by 1 dose level if chest CT findings are completely resolved Discontinue study drug if chest CT findings are not completely resolved

SARS-CoV-2 = severe acute respiratory syndrome coronavirus 2 (SARS-CoV-2); CT = computed tomography

a Closely monitor signs/symptoms after resuming DS-8201a, initially with a phone call every 3 days for the first week, and then with a weekly phone call thereafter, for a total of 6 weeks.

In addition to the recommendations outlined in [Table 17.4](#), Investigators may consider dose modifications of the study drug according to the subject's condition and after discussion with the study Medical Monitor or designee.

If an event is suspected to be drug-related ILD, manage per protocol ILD management guideline (Table 3.2).

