#### **5.4.1. Dose Interruptions**

The Investigator will evaluate which toxicities are attributed to the study drug and adjust the dose of the drug as recommended below. All dose modifications should be based on the worst preceding toxicity (NCI-CTCAE version 4.03). Specific criteria for interruption, re-initiation, dose reduction and/or discontinuation of DS-8201a are listed in Table 5.2. For Grade 3 or Grade 4 events, monitoring (including local lab tests when appropriate) should be performed at intervals no greater than 7 days until the AE is determined to be resolving or discontinuation of study treatment is decided.

Prophylactic or supportive treatment for expected toxicities, including management of study-drug induced AEs will be as per the treating physician's discretion and institutional guidelines.

In addition, Investigators may consider dose reductions or discontinuations of the study drug according to the subject's condition and after discussion with the Daiichi Sankyo's Medical Monitor or designee.

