### **6.3.15. Cycle 4 and All Subsequent Cycles, Day 1**

#### **6.3.15.1. Before Infusion**

The following procedures will be completed predose on Day 1:

- Record concomitant medications.
- Assess subjects for AEs.
- Obtain a serum or urine sample for pregnancy testing in women of childbearing potential. For postmenopausal subjects (no childbearing potential, as indicated by an elapse of at least 12 months after the last menstruation) or female subjects who have no possibility of pregnancy due to sterilization surgery, etc., no pregnancy test will be required. Female subjects who have been amenorrheic for 12 months or longer for medical reasons other than sterilization surgery (eg, effect of medication) will be regarded as women of child-bearing potential and required to undergo the pregnancy test.

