#### Pulmonary Assessments

- Pulmonary assessment will include CT or MRI of the chest, SpO2 and will be performed as described in schedule of events. For more details please refer to Section 6 of the protocol.
- An ILD AC will review all cases of ILD on an ongoing basis. Description of the ILD AC is available in Section 8.3.1 .

Additional safety assessments should be conducted as needed, at the Investigator's discretion.

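### As printed, Table 17.4 attaches its post-restart phone calls to the two same-dose restarts but not to the two reduced-dose restarts; the gap matters mainly from Cycle 4 on

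*Combined protocol and SAP*

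**What the plan says.** Section 17.7 presents the plan as advice: "the Sponsor recommends the following dose modification and management plan". Before any restart the subject must meet a recovery definition: free of symptoms, at least one negative RT-PCR, "and nearly or completely resolved chest CT findings".

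Table 17.4 then gives four ways to restart and one discontinuation:

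- Grade 1: same dose, footnote a marked.
- Grade 2, CT completely resolved: same dose, footnote a marked.
- Grade 2, CT not fully cleared: "Reduce by 1 dose level if chest CT findings are nearly resolved", no marker.
- Grade 3, CT cleared: "Reduce by 1 dose level if chest CT findings are completely resolved", no marker.
- Grade 3, CT not completely resolved: discontinue.

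Footnote a reads "Closely monitor signs/symptoms after resuming DS-8201a, initially with a phone call every 3 days for the first week", followed by weekly calls to a total of six weeks. Its wording does not mention dose. Below the table, suspected drug-related ILD is referred to Table 3.2.

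**The concern.** The marking runs against severity. Within Grade 2, the subject whose CT has cleared is called for six weeks, while the subject with residual CT findings has no calls marked. A Grade 1 subject is called and a Grade 3 subject is not. The documents give no reason for this, and they do not say that a dose reduction takes the place of symptom monitoring.

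Safety and tolerability is the primary objective, and Sections 1.4 and 3.2.5.2 name ILD/pneumonitis as an important identified risk. Table 3.2 starts the ILD work-up from radiographic changes or from new or worsening symptoms. Between scans, the pathway therefore starts only when someone learns of the symptom. A site that follows the markers literally could go a full cycle without asking.

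**Working it through.** The plan states no figure to reproduce. The check has two parts: whether another rule supplies the calls, and how much scheduled contact there is without them.

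**Other rules**

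- Section 5.4.1 requires monitoring at least every 7 days for Grade 3 or 4 events, but only "until the AE is determined to be resolving or discontinuation of study treatment is decided". The recovery definition means that this point has passed before a restart.
- Section 8.12 (Pulmonary Assessments) says "Additional safety assessments should be conducted as needed", at the investigator's discretion and with no interval. Section 6.3 says the same.
- Section 8.9 measures SpO2 before each Day 1 dose, so at the restart and then 21 days later.

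None of these is a dedicated contact schedule after restart.

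**Scheduled contact**

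Inputs: 21-day cycles (Section 3.2.2); Cycle 2 visits on Days 1, 8 and 15 (Sections 6.3.8 and 6.3.9); Cycle 3 visits on Days 1, 2, 4, 8 and 15 (Sections 6.3.11 to 6.3.13); after that only "Cycle 4 and All Subsequent Cycles, Day 1" (Section 6.3.15). Day 0 is the restart dose, given as Day 1 of its cycle, and no further delay is assumed. A visit on cycle Day d falls d − 1 days after that cycle's dose. The conditional Day 22 visits are left out, because they apply only when the next cycle is delayed or not given.

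Footnote a, counted from day 0: days 3, 6, 14, 21, 28, 35 and 42, which is 7 calls, 3 of them by day 20. If the weekly calls run from day 6: days 3, 6, 13, 20, 27, 34 and 41, again 7 calls, 4 of them by day 20. If week 1 is counted as days 1, 4 and 7, the total is 8, with 4 by day 20.

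| Restart at | Routine visits (day) | By day 20 | By day 42 | Longest gap |
|---|---|---|---|---|
| Cycle 2 | 7, 14, 21, 22, 24, 28, 35, 42 | 2 | 8 | 7 days |
| Cycle 3 | 1, 3, 7, 14, 21, 42 | 4 | 6 | 21 days (day 21 to 42) |
| Cycle 4 or later | 21, 42 | 0 | 2 | 21 days |
| Footnote a alone | 3, 6, 14, 21, 28, 35, 42 | 3 (or 4) | 7 (or 8) | 8 days |

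With footnote a added to a restart at Cycle 4 or later, the longest gap between contacts falls from 21 days to 8 (day 6 to day 14).

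Scheduled tumor imaging adds little. It is due every 6 weeks for the first 24 weeks and every 12 weeks after that (Section 6.3.1). The average number of scans in the first 20 days is 20/42 = 0.48 in the first period and 20/84 = 0.24 later.

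**The case against.** **The markers may simply have been lost.** The table was read from a PDF, and superscripts elsewhere in that text are unreliable. In Table 17.3 the laboratory row carries the letter of a PK timing note, and notes e, j and t are defined but have no surviving marker. Against this, both same-dose markers in Table 17.4 came through, one of them in the same Grade 2 cell as an unmarked line. The doubt is real but does not remove the point, and a look at the page settles it.

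**The pattern may be deliberate.** It fits a rule in which full-dose restarts get calls and riskier restarts get lower exposure, with discontinuation when CT has not cleared after Grade 3. The documents do not state that rule. Lower exposure also does not detect symptoms, so the two measures are not alternatives.

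**The footnote may cover every restart.** Its text is not limited by dose, and a site could apply it to all four lines. That is a fair reading. But the markers show where a footnote applies, and the unmarked lines speak of reducing, not resuming. If all restarts were meant, the markers need correcting anyway.

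**Other safeguards apply.** The recovery definition, the SpO2 checks and the referral to Table 3.2 hold at any dose. The first acts before the restart, the second is 21 days apart, and the third depends on the subject reporting a symptom. They narrow the gap without closing it.

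**A reader might infer that these subjects have no scheduled contact after restart.** The documents do not support that. After a Cycle 3 restart there are 4 routine visits in the first 20 days, at least as many as the calls. After a Cycle 2 restart there are 2 by day 20 and 8 by day 42.

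**Conclusion.** The point holds as a minor one. As printed, the two reduced-dose restarts carry no dedicated contact schedule, and routine visits do not make up for that early on when the restart falls at Cycle 4 or later: 0 visits against 3 or 4 calls in the first 20 days, and 2 visits against 7 calls over 42 days. Such restarts can occur, because the number of cycles is not fixed. For restarts at Cycle 2 or 3 little early contact is lost.

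Few if any of about 12 subjects would be affected. The documents give no infection rate, and they do not say how many subjects were still on treatment when the SARS-CoV-2 provisions took effect. A delay of more than 28 days means withdrawal (Sections 3.2.2 and 5.4.2), which reduces the number further.

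A reader might also infer that the safety results would be biased. The documents do not support that: the safety analysis is descriptive, and no estimate, sample size or analysis changes.

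The conclusion rests on the markers being as printed and on 21-day cycles without further delay after restart. Confidence is medium, because of the superscript question.

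**What to change.** Attach footnote a to both reduced-dose restart lines of Table 17.4: Grade 2 with nearly resolved CT, and Grade 3 with completely resolved CT. The change is the same whether the omission was a slip or a choice. It costs two footnote markers and about 7 phone calls per affected subject. If the source page already shows the markers, no change is needed.
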